Attachment 1: MAYO SCORE

Mayo scoring system for assessment of ulcerative colitis activityStool frequency^a

- 0 = Normal number of stools for this patient
- 1 = 1-2 stools more than normal
- 2 = 3-4 stools more than normal
- 3 = 5 or more stools more than normal

Rectal bleeding^b

- 0 = No blood seen
- 1 = Streaks of blood with stool less than half the time
- 2 = Obvious blood with stool most of the time
- 3 = Blood alone passed

Findings of endoscopy

- 0 = Normal or inactive disease
- 1 = Mild disease (erythema, decreased vascular pattern, mild friability)
- 2 = Moderate disease (marked erythema, absent vascular pattern, friability, erosions)
- 3 = Severe disease (spontaneous bleeding, ulceration)

Physician's global assessment^c

- 0 = Normal
- 1 = Mild disease
- 2 = Moderate disease
- 3 = Severe disease

^a At the screening visit, each person indicates the number of stools he/she passed in a 24-hour period when in remission or before his/her UC diagnosis, thereby serving as his/her own control to establish the degree of abnormality of stool frequency.

^b The daily bleeding score represents the most severe bleeding of the day.

^c The physician's global assessment acknowledges the 3 other criteria, the patient's recall of abdominal discomfort and general sense of well-being, and other observations, such as physical findings and the patient's performance status.

Attachment 2: PROHIBITED CHANGES IN UC MEDICATIONS (ICE 2)

The following are the-protocol-prohibited changes in UC medication(s):

(i) Restricted or prohibited medications

- Initiation of restricted or prohibited medications or therapies as defined in the protocol (see Protocol Section 6.5.2), except for antibiotics used to treat UC, TPN, and apheresis

(ii) Oral corticosteroids**Over the Combination Comparison Phase (Through Week 12)**

- Initiation of oral corticosteroids (including budesonide and beclomethasone dipropionate) due to worsening of disease after the baseline visit for participants who were not receiving oral corticosteroids at baseline
- Increase in the dose of oral corticosteroids (including budesonide and beclomethasone dipropionate) above the baseline dose, as specified below, due to worsening of disease
 - i. Oral corticosteroids > 5 mg/day (prednisone equivalent)
 - ii. Oral budesonide > 3 mg/day
 - iii. Oral beclomethasone dipropionate > 5 mg/day
- Any switch among oral budesonide, oral beclomethasone dipropionate or other oral corticosteroids (excluding prednisone equivalent changes) due to worsening of disease

Over the Monotherapy Phase (After Week 12 Through Week 38)

- Initiation of oral corticosteroids (including budesonide and beclomethasone dipropionate) due to worsening of disease that lasts for more than 7 days after the Week 26 visit (i.e., approximately 90 days prior to Week 38) for participants who were not receiving oral corticosteroids at baseline
- Increase in the dose of oral corticosteroids (including budesonide and beclomethasone dipropionate) above the baseline dose, as specified below, due to worsening of disease for more than 7 days after the Week 26 visit (i.e., approximately 90 days prior to Week 38).
 - i. Oral corticosteroids > 5 mg/day (prednisone equivalent)
 - ii. Oral budesonide > 3 mg/day
 - iii. Oral beclomethasone dipropionate > 5 mg/day
- Initiation of oral corticosteroids (including budesonide and beclomethasone dipropionate) due to reasons other than worsening of disease that lasts for more than 28 days after the Week 26 visit (i.e., approximately 90 days prior to Week 38) for participants who were not receiving oral corticosteroids at baseline
- Increase in the dose of oral corticosteroids (including budesonide and beclomethasone dipropionate) above the baseline dose, as specified below, due to reasons other than worsening of disease for more than 28 days after the Week 26 visit (i.e., approximately 90 days prior to Week 38)
 - i. Oral corticosteroids > 5 mg/day (prednisone equivalent)
 - ii. Oral budesonide > 3 mg/day

iii. Oral beclomethasone dipropionate > 5 mg/day

- Any switch among oral budesonide, oral beclomethasone dipropionate or other oral corticosteroids (excluding prednisone equivalent changes) due to worsening of disease

(iii) 5-ASA compounds

- Initiation of oral or rectal 5-ASA compounds due to worsening of disease
- Increase above baseline in the dosage of oral 5-ASA compounds due to worsening of disease
- Change from one oral 5-ASA compound to another 5-ASA compound due to worsening of disease

Attachment 3: GRADING CRITERIA FOR THE HISTOLOGICAL EVALUATION OF DISEASE ACTIVITY IN ULCERATIVE COLITIS

Grade 0	Structural (architectural change)
Subgrades	
0.0	No abnormality
0.1	Mild abnormality
0.2	Mild or moderate diffuse or multifocal abnormalities
0.3	Severe diffuse or multifocal abnormalities
Grade 1	Chronic inflammatory infiltrate
Subgrades	
1.0	No increase
1.1	Mild but unequivocal increase
1.2	Moderate increase
1.3	Marked increase
Grade 2	Lamina propria neutrophils and eosinophils
2A Eosinophils	
2A.0	No increase
2A.1	Mild but unequivocal increase
2A.2	Moderate increase
2A.3	Marked increase
2B Neutrophils	
2B.0	None
2B.1	Mild but unequivocal increase
2B.2	Moderate increase
2B.3	Marked increase
Grade 3	Neutrophils in epithelium
3.0	None
3.1	< 5% crypts involved
3.2	< 50% crypts involved
3.3	> 50% crypts involved
Grade 4	Crypt destruction
4.0	None
4.1	Probable—local excess of neutrophils in part of crypt
4.2	Probable—marked attenuation
4.3	Unequivocal crypt destruction
Grade 5	Erosion or ulceration
5.0	No erosion, ulceration, or granulation tissue
5.1	Recovering epithelium+adjacent inflammation
5.2	Probable erosion—focally stripped
5.3	Unequivocal erosion
5.4	Ulcer or granulation tissue

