6.5.1. Concomitant Medications

Immunomodulators (6-MP, AZA, and MTX) must be discontinued 2 weeks prior to the first dose of study intervention, as defined in the Inclusion Criteria (Section 5.1). Participants who are receiving oral 5-ASA compounds or oral corticosteroids for the treatment of UC at baseline should maintain a stable dose for the specified period before baseline, as defined in the Inclusion Criteria (Section 5.1). In general, participants who are receiving these medications for UC at baseline (ie, Week 0) should maintain a stable dose through Week 38, with the exception of oral corticosteroids. Therapies can only be discontinued or reduced in dose after Week 0 if investigator judgment requires it because of toxicity or other medical necessity; even if the toxicity resolves, the therapy should not be restarted. Oral corticosteroids must be maintained at baseline doses through Week 6, and all participants must begin tapering oral corticosteroids at Week 6, unless medically not feasible (see further details in Section 6.5.1.1, Oral Corticosteroids Tapering).

Enrolled participants **should not initiate** any of the following concomitant UC-specific medical therapies:

- Oral or rectal 5-ASA compounds.
- Oral, parenteral, or rectal corticosteroids, including budesonide and beclomethasone dipropionate.
- Antibiotics as a primary treatment for UC.
- Total parenteral nutrition or enteral nutrition as a treatment for UC.

If the above medical therapies are initiated or medication doses are changed based on medical necessity as assessed by the investigator, participants should continue to attend all study visits and have all assessments. While this does not represent a deviation from the study protocol and the participants may remain on their assigned therapy, it may be considered a treatment failure. Treatment failures due to UC medication changes will be defined in the SAP.

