6.5.2. Prohibited Concomitant Medications

Participants who initiate the following treatments during study participation will have their study intervention discontinued:

- Immunomodulatory agents (including, but not limited to, 6-MP, AZA, MTX, tofacitinib, 6-thioguanine, cyclosporine, mycophenolate mofetil, tacrolimus, and sirolimus).
- Immunomodulatory biologic agents (including, but not limited to, TNF antagonists, ustekinumab, vedolizumab, abatacept, anakinra).
- Experimental IBD medications (including, but not limited to, upadacitinib, filgotinib, ozanimod, etrolizumab, brazikumab, mirikizumab, risankizumab) or other investigational therapies.
- Thalidomide or related agents.

The sponsor or designee must be notified in advance (or as soon as possible thereafter) of any instances in which prohibited therapies are administered.

As protection of human research participants is paramount, it is recognized that initiating such therapies may rarely be required due to medical necessity. However, initiation of these prohibited medications should be documented as a deviation from the study protocol, and participants will be discontinued from receiving further study intervention (Section 7).

Participants who discontinue study intervention administration should complete the appropriate visit(s) as described in Section 1.3.

Note: Participants must not receive guselkumab or golimumab outside of the protocol or participate in any other clinical study with an investigational agent while in this study, and must terminate study participation if they do. Prior to termination of study participation, participants should complete the appropriate visit(s) as described in Section 1.3.

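### SAP Attachment 2 item (i) has a defective cross-reference, so whether a parenteral or rectal corticosteroid started for worsening UC before Week 12 is ICE 2 depends on how the citation is read

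*SAP*

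**What the plan says.** SAP 5.3.2 defines ICE 2 through Attachment 2 alone. It handles ICEs 1 to 3 by the composite strategy, on the ground that they are an unfavorable outcome. Attachment 2 has three items:

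- Item (i) counts the start of restricted or prohibited medications "as defined in the protocol (see Protocol Section 6.5.2), except for antibiotics used to treat UC, TPN, and apheresis".
- Item (ii) deals with corticosteroids, and every bullet is about oral products. Through Week 12 the initiation bullet covers starts "due to worsening of disease after the baseline visit for participants who were not receiving oral corticosteroids at baseline".
- Item (iii) deals with 5-ASA and includes "Initiation of oral or rectal 5-ASA compounds due to worsening of disease".

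The protocol splits concomitant UC therapy into two lists. Section 6.5.1 names therapies that should not be started, among them "Oral, parenteral, or rectal corticosteroids, including budesonide and beclomethasone dipropionate", antibiotics as primary UC treatment, and "Total parenteral nutrition or enteral nutrition as a treatment for UC". Of a participant who starts one, it says "the participants may remain on their assigned therapy, it may be considered a treatment failure", and then: "Treatment failures due to UC medication changes will be defined in the SAP". Section 6.5.2 is a separate list of immunomodulatory agents, immunomodulatory biologics, experimental or investigational drugs, and thalidomide. It opens with "Participants who initiate the following treatments during study participation will have their study intervention discontinued".

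**The concern.** The section that item (i) cites does not contain what item (i) exempts. UC antibiotics and TPN are in Protocol 6.5.1, and apheresis appears only in exclusion criterion 12f. Protocol 6.5.2 also names no corticosteroid. The protocol leaves the definition of treatment failure to the SAP, so the SAP text controls, and its wording leaves parenteral and rectal corticosteroids without a rule.

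The literal outcome is hard to defend. A participant whose UC worsens and who starts rectal 5-ASA is a non-responder. So is one who starts an oral steroid without having been on one at baseline. A participant given an intravenous or rectal steroid for the same reason, who stays on study drug, is scored on the observed Week 12 Mayo score. That conflicts with the stated reason for the composite strategy. Two programmers could also classify the same participant differently on the primary endpoint, depending on whether they follow the citation or its apparent purpose.

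**Working it through.** **Step 1: the lists side by side.** Each row is a therapy started for worsening UC before Week 12 by a participant who stays on study drug.

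| Therapy started | In 6.5.1 | In 6.5.2 | Attachment 2, literal | Item (i) read as all of 6.5 |
|---|---|---|---|---|
| Parenteral or rectal corticosteroid | yes | no | not ICE 2 | ICE 2 |
| Oral corticosteroid, none at baseline | yes | no | ICE 2, item (ii) | ICE 2 |
| Rectal 5-ASA | yes | no | ICE 2, item (iii) | ICE 2 |
| UC antibiotic | yes | no | not ICE 2 | not ICE 2 (exempt) |
| TPN | yes | no | not ICE 2 | not ICE 2 (exempt) |
| Enteral nutrition for UC | yes | no | not ICE 2 | ICE 2 (only TPN is exempt) |
| Apheresis | no | no | not ICE 2 | not ICE 2 (exempt) |

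The first row is the ambiguity. The enteral nutrition row shows that simply adding 6.5.1 to the citation would create a new, unintended ICE.

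**Step 2: can 6.5.2 be stretched to cover steroids?** Its immunomodulatory-agents entry is open-ended. But starting a 6.5.2 agent ends study treatment, whereas 6.5.1 lets steroid starters continue. Reading steroids into 6.5.2 would contradict 6.5.1.

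**Step 3: who would be rescored.** Only a participant who starts a parenteral or rectal steroid for worsening before Week 12, has no other ICE in categories 1 to 3, and still meets clinical response on the observed Week 12 data.

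**Step 4: reproduce the plan's power.** The inputs are from Protocol 9.2: n = 70 per arm, response 55/55/75%, 1-sided 0.1 for each comparison, both required. Simulating three binomial arms (400,000 trials, chi-square without continuity correction) gives 81.4% against the stated 81%. The other five Table 4 rows also reproduce (stated/computed): 79/79.2, 66/65.9, 69/69.1, 90/89.8, 85/85.4. With the CMH test stratified by steroid use (strata of 28 and 42 per arm, an assumption, with equal rates in both), joint power is 80.9%.

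**Step 5: what one participant is worth.** One responder is 1/70 = 1.43 percentage points of an arm. Unstratified, z = (difference in proportions) / √[p(1−p)·2/70], with p the pooled rate, compared with 1.282:

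- 39/70 against 47/70: p = 86/140 = 0.614, z = 0.1143/0.0823 = 1.39, significant.
- 39/70 against 46/70: p = 85/140 = 0.607, z = 0.1000/0.0826 = 1.21, not significant.

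So a single reclassification matters only when a result sits at the boundary.

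**Step 6: how often the verdict changes.** Responders rescored as non-responders, stratified CMH, 400,000 trials at 55/55/75%, assumed range 0 to 2 per arm:

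| Rescored (golimumab, guselkumab, combination) | Verdict changes |
|---|---|
| 1, 1, 1 | 0.43% |
| 2, 2, 2 | 0.69% |
| 1, 0, 0 | 2.27% |
| 0, 1, 0 | 2.24% |
| 1, 1, 0 | 4.68% |
| 0, 0, 1 | 6.04% |

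Rescoring only in monotherapy arms turns negative trials positive. Rescoring only in the combination arm does the opposite.

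**The case against.** The best reply is that the intent is plain. Item (i) is headed as covering both restricted and prohibited medications, and Protocol 5.3 points to 6.5 as a whole for both kinds. Exempting UC antibiotics and TPN makes sense only if the 6.5.1 list was meant. On that reading parenteral and rectal steroids are already ICE 2. This stands as evidence of intent. It does not settle the text, because taking in all of 6.5.1 would also make any oral steroid or 5-ASA start an ICE and override the worsening and baseline conditions in items (ii) and (iii). No order of precedence is stated.

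A second reply is that other rules catch many of these participants. Stepping down to an oral steroid for worsening triggers item (ii) in baseline non-users, and in baseline users whose dose rises past the threshold. Stopping study drug for lack of efficacy or an AE of worsening UC is ICE 3, and Protocol 7.1 says discontinuation must be strongly considered for worsening UC. This narrows the group by an amount the documents do not give. A rectal-only course with study drug continued is not caught.

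A third reply is that SAP 5.5 has steroid-free Week 12 endpoints. They show steroid use at Week 12 and miss a course that ended earlier. They also count as failures participants whose taper ran late. From 20 mg/day, Protocol Table 3 takes six weekly steps (15, 10, 7.5, 5, 2.5, 0), reaching zero at Week 11 if the first is at Week 6, so a two-week pause leaves the participant on steroid at Week 12.

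A reader might go further and infer that the sponsor chose to exempt parenteral and rectal steroids, or that the primary comparison is biased towards one arm. The documents support neither. The exceptions point to a citation slip, and nothing is said about how often such starts occur or in which arm.

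**Conclusion.** The cross-reference is defective, and as written it leaves the handling of parenteral and rectal steroid rescue open on the primary endpoint. The literal text allows such a participant to be a responder; the probably intended reading makes the same participant a non-responder. This goes beyond missing detail, because the literal rule conflicts with the estimand's own rationale.

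The size and direction of the effect are unknown, since the plan gives no rescue counts. With equal rescoring of one or two responders per arm the verdict changes in about 0.4% to 0.7% of trials, so the effect is probably small. The 2% to 6% figures need one-sided splits for which the documents give no support and should not be read as estimates. All of these rest on the planned 55/55/75% rates, the assumed strata and the assumed range of 0 to 2 per arm. The point is worth correcting because the repair is cheap, not because a large distortion has been shown.

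**What to change.** 1. Keep the 6.5.2 citation in item (i) and do not add 6.5.1 to it.
2. Retitle item (ii) as Corticosteroids and add one bullet: *starting a parenteral or rectal corticosteroid because of worsening disease, after the baseline visit and through Week 12, is ICE 2 regardless of baseline oral corticosteroid use.*
3. For Week 38, apply the limits of the existing oral-steroid rules for worsening: more than 7 days, after the Week 26 visit.
4. Delete the three exceptions that refer to nothing in 6.5.2, or state separately that UC antibiotics, TPN and apheresis are not ICEs.
5. Have staff blinded to treatment assignment finalise the wording before the Week 12 lock, since SAP 1.5 records that some sponsor staff have seen unblinded interim data. Report the number of affected participants by arm.

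The cost is a few lines of SAP text. Protocol 6.5 already requires route, treatment period and indication to be recorded, so no new data are needed. The downside is that any such starters become non-responders, including baseline oral-steroid users given a rectal course. A baseline user who only goes back up to the baseline oral dose during the taper, which Protocol 6.5.1.1 permits, would not fail. The sponsor should accept that asymmetry knowingly.

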5.5. Other Efficacy Endpoints

In addition to the primary and major secondary endpoints, other efficacy endpoints related to disease status, HRQoL outcomes (including fatigue), and inflammatory biomarkers will also be analyzed. This section outlines the definitions (Section 5.5.1) and analyses (Section 5.5.2) of the other efficacy endpoints.

Clinical Endpoints

- Clinical response at Week 38

-
- Clinical response at Week 38 by clinical response status at Week 12
 - Clinical remission at Week 38
 - Clinical remission at Week 38 by clinical remission status at Week 12
 - Clinical remission at Week 38 by clinical response status at Week 12
 - Change from baseline in Mayo score at Weeks 12 and 38.
 - Change from baseline in partial Mayo score by visit through Week 38.
 - Change from baseline in modified Mayo score at Weeks 12 and 38.
 - Change from baseline in Mayo subscores by visit through Week 38.
 - Modified Mayo response at Weeks 12 and 38
 - Modified Mayo response at Week 38 by modified Mayo response status at Week 12
 - Symptomatic remission by visit through Week 38
 - Endoscopic healing at Weeks 12 and 38
 - Endoscopic healing at Week 38 by endoscopic healing status at Week 12
 - Endoscopic normalization at Weeks 12 and 38.
 - Endoscopic normalization at Weeks 38 by endoscopic normalization status at Week 12
 - Clinical response, clinical remission, and endoscopic healing at Weeks 12 and 38 by negative response signature status at baseline.
 - Clinical remission by alternative definitions:
 - Clinical remission (UNIFI definition) at Weeks 12 and 38
 - Clinical remission (UNIFI definition) at Week 38 by clinical remission (UNIFI definition) status at Week 12
 - Clinical remission (Health Authority definition 1) at Weeks 12 and 38
 - Clinical remission (Health Authority definition 1) at Week 38 by clinical remission (Health Authority definition 1) status at Week 12
 - Clinical remission (Health Authority definition 2) by visit at Weeks 12 and 38
 - Clinical remission (Health Authority definition 2) at Week 38 by clinical remission (Health Authority definition 2) status at Week 12
 - Histologic healing at Weeks 12 and 38
 - Mucosal healing at Weeks 12 and 38
 - Histologic remission at Weeks 12 and 38
 - Histologic-endoscopic mucosal healing at Weeks 12 and 38
 - Deep histologic-endoscopic mucosal healing at Weeks 12 and 38
 - Geboes total score, high activity subscore, and low activity subscore at Weeks 0, 12, and 38

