5.5.2. Estimands

Unless otherwise specified, the attributes and strategies for the ICEs that were used for the primary estimand of the primary endpoint (Estimand 1, Section 5.3.2) will also be used for the estimand for each of the other endpoints (Section 5.5).

ICE categories 1-3 will be handled by the **composite strategy**. ICE category 4 will be handled by the **hypothetical strategy** (as if participants would have not experienced this intercurrent event), and ICE category 5 will be handled by the **treatment policy strategy**. To be more specific,

- Participants with an ICE in category 1-3 prior to a visit will be considered, at that visit and all subsequent visits, as **not having achieved the binary endpoints for binary endpoints** and as **having no change from baseline (i.e., the baseline value will be assigned) for continuous endpoints**.
- Participants with an ICE 4 will have their observed data set to missing at all visits after the ICE 4.
- Participants with an ICE 5 will have their observed data used after the ICE 4 used, if available.
- For participants experiencing multiple ICEs, ICEs in categories 1-3 will override ICEs 4 and 5.

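### Oral steroid rescue that begins after Week 12 and ends by about Week 26 meets no initiation or increase rule for ICE 2, so on-rescue data can count as success at Weeks 14 to 26

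*SAP*

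**What the plan says.** SAP Attachment 2 defines ICE 2, the prohibited changes in UC medication, separately for the two study phases.

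- **Through Week 12.** An oral steroid start counts if it is "due to worsening of disease after the baseline visit for participants who were not receiving oral corticosteroids at baseline". No minimum duration applies. Increases beyond listed increments and switches among oral steroids, when due to worsening, also count.
- **After Week 12.** A start for worsening counts only if it is "due to worsening of disease that lasts for more than 7 days after the Week 26 visit", and an increase only if it is "due to worsening of disease for more than 7 days after the Week 26 visit". For other reasons, a start must be one "that lasts for more than 28 days after the Week 26 visit". The cut is explained as "approximately 90 days prior to Week 38".
- **After Week 12, switches.** A switch among oral steroids for worsening counts with no Week 26 limit.
- **5-ASA, any time.** The list includes "Initiation of oral or rectal 5-ASA compounds due to worsening of disease", again with no time limit or minimum duration.

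SAP Section 5.5.2 applies these events to all other efficacy endpoints: "Participants with an ICE in category 1-3 prior to a visit will be considered, at that visit and all subsequent visits", as failures for binary endpoints and at their baseline value for continuous ones. Section 5.5 lists "Symptomatic remission by visit through Week 38", along with partial Mayo, IBDQ and PROMIS measures by visit. Section 5.5.3 compares combination with each monotherapy at each visit through Week 38.

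**The concern.** The Week 26 cut is built around Week 38, yet the same event list governs every visit in between. A participant who needs oral steroids for worsening at Week 14 and finishes them by Week 25 has no ICE 2 from that course, even at visits when the steroid is being taken. The observed score is used. The plan otherwise treats rescue for worsening as failure, both for steroids through Week 12 and for 5-ASA at any time.

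The interval matters. The combination arm receives its last golimumab dose at Week 10 and continues on guselkumab alone, and how that sequence performs is a secondary objective. If rescue use differs between arms at Weeks 14 to 26, the by-visit comparisons mix the effect of study treatment with that of the steroid. Symptomatic remission as defined in Section 5.5.1.1.2 has no steroid condition, and steroid-free endpoints are listed only at Weeks 12 and 38.

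**Working it through.** **1. The plan's own figure.** Week 26 to Week 38 is 12 × 7 = 84 days. With the ±4-day window at each visit (Protocol Section 1.3, Table 2), the range is 84 ± 8 = 76 to 92 days. The stated figure of about 90 days is consistent. The cut is a look-back window for Week 38.

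**2. Length of the uncovered interval.** Week 12 to Week 26 is 14 × 7 = 98 days, or 105 with the 7-day allowance. The monotherapy phase is 26 × 7 = 182 days. The shares are 98/182 = 54% and 105/182 = 58%.

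**3. Visits affected.** Table 2 schedules ten visits: Weeks 14, 16, 18, 22, 24, 26, 30, 32, 34 and 38. Six fall at or before Week 26, and partial Mayo is collected at all six. IBDQ and PROMIS are collected only at Weeks 24 and 38, so one of their visits is affected.

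**4. Rules side by side**, for a participant not on oral steroids at baseline, except in the switch row:

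| Event, due to UC worsening | Rule met | Result under Section 5.5.2 |
|---|---|---|
| Oral steroid start at Week 11 | ICE 2, rule through Week 12 | Failure from then on, including Week 38 |
| 5-ASA start at Week 14 | ICE 2, 5-ASA rule | Failure from then on, including Week 38 |
| Switch among oral steroids at Week 14 | ICE 2, switch rule | Failure from then on, including Week 38 |
| Study intervention stopped for inefficacy or worsening | ICE 3 | Failure from then on, including Week 38 |
| Oral steroid course, Week 14 to Week 25 | None | Observed data used at every visit |

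The post-Week 12 wording could mean a course running past Week 26 or one started after it. The last row holds on either reading.

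**5. Does another clause catch it?** Clause (i) of Attachment 2 points to Protocol Section 6.5.2, which does not list corticosteroids. They appear in Section 6.5.1, which leaves the definition of treatment failure to the SAP. Clause (i) also excepts antibiotics and parenteral nutrition, which are 6.5.1 items, so one could argue that it reaches 6.5.1. But if it reached oral steroids, the time limits in clause (ii) would have no effect on starts.

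**6. Size.** The documents give no rescue rates, so this step is an illustration. Let r be the share of an arm on uncounted rescue at a visit and q the share of those who meet the endpoint. Treating them as failures lowers the arm's rate by r × q.

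- Low: 0.05 × 0.25 = 0.0125, or 1.3 points (0.9 of 70 participants).
- Middle: 0.10 × 0.50 = 0.05, or 5 points (3.5 of 70).
- High: 0.15 × 0.75 = 0.1125, or 11.3 points (7.9 of 70).
- Between arms, with r of 5% in one and 15% in the other and the same q: (0.15 − 0.05) × q = 2.5 to 7.5 points for q of 25% to 75%. Equal r and q cancel.

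**The case against.** The strongest reply is that this is a choice of estimand. Protocol Section 6.5.1 says such changes are not deviations and may, not must, be treated as failure. The SAP then wrote an explicit rule with an explicit anchor, and using observed data during a finished steroid course is defensible. The stakes are also low: these are other endpoints with nominal, unadjusted p-values, and on-trial oral steroid use is summarised by treatment group (SAP Section 4.6).

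Much of this stands, and it keeps the point minor. It does not remove it. The plan's declared strategy for ICE 2 is composite, and the only reason given for the cut concerns Week 38. Nothing explains its use at Weeks 14 to 26, and a summary of steroid use does not show its effect on an endpoint.

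A reader might infer more than the documents support:

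- **That steroid rescue in this interval never counts.** Switches for worsening are ICE 2 throughout, and stopping study intervention for inefficacy or worsening is ICE 3.
- **That everyone on rescue is scored a success.** They must still meet the criteria, and missing status on a binary endpoint is non-response.
- **That any 5-ASA start is failure.** It is so only when due to worsening.
- **That loss of response after golimumab stops is being hidden.** The documents do not show that rescue is most frequent in these weeks or more frequent in any arm. Monotherapy-phase full Mayo, endoscopic and histologic endpoints are assessed at Week 38.

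**Conclusion.** The gap is real but narrow. An oral steroid start, or an increase beyond the listed increments, for worsening UC that begins after Week 12 and ends within about 7 days after Week 26 meets no initiation or increase rule for ICE 2. Data on that rescue are used as observed, which does not fit the rule through Week 12 or the 5-ASA rule.

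It affects six visits for symptomatic remission and partial Mayo measures, and Week 24 for IBDQ and PROMIS. The Week 12 primary and major secondary endpoints are untouched, and the Week 26 rule is coherent for Week 38.

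The size is unknown. The range of 1.3 to 11.3 points for one arm rests entirely on the assumed 5-15% on rescue and 25-75% of those meeting the endpoint. The direction and size of any between-arm effect depend on differential use, about which the documents say nothing. This is a worthwhile clarification of non-key analyses, not a threat to the trial's main conclusions.

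**What to change.** Keep the Week 26 rule for Week 38 endpoints. In both Attachment 2 and Section 5.5.2, define for by-visit endpoints at Weeks 14 to 26 a visit-specific ICE 2 flag: oral steroids started, or raised beyond the listed increments, because of UC worsening and ongoing at that visit. State it as an exception to the carry-forward in Section 5.5.2. Without that exception, a Week 14 course would become failure at Week 38 and override the rule being kept.

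At minimum, add a by-visit analysis of symptomatic remission without rescue corticosteroids for Weeks 14 to 26.

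Two related points should be settled in the same edit: the date of the event when a course starts before Week 26 and runs more than 7 days past it, and the clause (i) pointer to Protocol Section 6.5.2, given that its exceptions include 6.5.1 items.

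The cost is an edit to two SAP sections and a flag from medication data already recorded (Protocol Section 6.5). By-visit rates may be slightly lower. Values assigned for continuous endpoints would enter the shared MMRM and could affect its Week 38 estimates, so the flag could be limited to binary endpoints. It is an analysis flag only and changes no treatment rule.
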